## 8.2.3. Efficacy Evaluable Population

All patients who complete at least one post-baseline disease status assessment or who discontinue study medication early due to study drug-related toxicity will be considered evaluable for efficacy. Patients who discontinue and have not received at least 85% of the telaglenastat doses and at least 5 doses of azacitidine within the first cycle of treatment will be considered non-evaluable for response and may be replaced.

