#### 4.1.1. Phase 1b:

In the Phase 1b portion, telaglenastat will be administered at the goal starting dose level 0 of 600mg BID continuously. The MTD is defined as the highest dose level with </= 1 out of 6 patients experiencing a DLT during the first cycle.

The first 6 patients will be treated at dose level 0. If </= 1 out of the 6 patients experience a DLT during the first cycle, this level will be identified as the RP2D and the study will progress to the Phase II portion. If > 2 out of the 6 patients experience a DLT during the first cycle, this dose level would exceed the MTD, and an additional 6 patients will be treated at the next lower dose level. Reduced dose level -1 is defined in Table 1 below. Patients treated in the Phase 1b portion that are removed from study before day 28 for any reason other than toxicity, and have not experienced DLT, will be replaced.

AZA will be administered subcutaneously (SQ) or intravenously (IV) for 7 days of every cycle (days 1-7) as determined by the treating physician. Both SQ and IV forms of administration are FDA-approved and are considered interchangeable, based on patient and physician preference.

Table 1: Dose de-escalation for telaglenastat and AZA

Dose Level	CB-839 (oral)	AZA (IV or SQ)
0	600 mg BID days 1-28	75 mg/m2 days 1-7
-1	400 mg BID days 1-28	75 mg/m2 days 1-7

Dose reductions beyond those mentioned in this table or different to the doses specified should be discussed with the PI and documentation of the justification recorded in the medical record.

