#### 4.1.2. Phase II:

The Phase II portion will open after determination of the RP2D of the combination of telaglenastat and AZA from the Phase 1b portion. The RP2D will be selected based on the totality of the clinical data (safety, tolerability, PK, PDn, and efficacy) and will not exceed the MTD. A total of 28 evaluable MDS patients, which includes 22 Phase II patients and 6 patients treated at the RP2D from Phase 1, will be enrolled. We will enroll 16 patients in the first stage. If 6 or fewer patients achieve response, enrollment will be halted. If 7 or more out of the first 16 patients achieve response, accrual will continue until a total of 28 patients have been enrolled. If 15 or more out of these 28 patients achieve response, the treatment will be considered efficacious and worthy of further investigation. Toxicities will be monitored closely using the method of Thall et al (1995) in Section 8.1.3.

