#### 5.2.3. Cycle 1 Day 8, Day 15, Day 22 (+/- 3 days)

At these Cycle 1 mid-cycle assessments, patients will return to clinic to undergo the following procedures:

NCT ID: NCT03047993

Protocol 2016-0636 ate: 06/03/2019 Version 1

Page **21** of **39** 

- 1. AE monitoring
- 2. Recording of concomitant medications
- 3. Vital signs and weight
- 4. Symptom-directed physical exam
- 5. Clinical laboratory evaluation (hematology, serum chemistries)
- 6. Plasma samples for PK analysis pre-dose on C1D15
- \*Patients may take their telaglenastat doses prior to, during, or after their clinic visit according to their usual dosing schedule because there are no specified pre-dose procedures *with the exception of C1D15* where the patient should not take their telaglenastat dose prior to arrival due to pre-dose PK sample.

## 5.2.4. Cycle 2 Day 1 (+/- 5 days) and all subsequent cycles on Day 1

Patients may take their telaglenastat doses prior to, during, or after their clinic visit according to their usual dosing schedule because there are no specified pre-dose study procedures *with the exception of C2D1 and C3D1* due to pre-dose PK samples.

- 1. Vital signs and weight
- 2. AE monitoring
- 3. Recording of concomitant medications
- 4. Symptom-directed physical exam
- 5. Clinical laboratory values (hematology, serum chemistry)
- 6. Plasma sample for exploratory biomarker analysis
- 7. Bone marrow evaluation of tumor/disease burden is required for all patients receiving telaglenastat on cycle 2 day 1, cycle 4 day 1, cycle 6 day 1, and every 3 cycles thereafter, +/- 5 days for all above assessments. Additional evaluations are acceptable as clinically indicated.
- 8. Bone marrow sample for biomarker and pharmacodynamics analysis during above protocol-defined time points.
- 9. Plasma samples for correlative analysis on same day as bone marrow sample timepoints are collected
- 10. Plasma samples for PK analysis prior to the administration of study drug, on C2D1 and C3D1.

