#### 6. RESPONSE DEFINITIONS

### **6.1 Study Endpoints:**

**6.2.1. Efficacy Analysis:** Clinical activity of telaglenastat + AZA will be assessed based on Modified IWG Response Criteria for MDS (Cheson et al, 2006).

Proposed Modified International Working Group Response Criteria for Altering Natural History of MDS Category	Response criteria (Responses must last at least 4 weeks)
Complete remission	Bone marrow: ≤5% myeloblasts with normal maturation of all cell lines* Persistent dysplasia will be noted*† Peripheral blood‡ Hgb ≥11 g/dL Platelets ≥100 × 109/L Neutrophils ≥1.0 × 109/L† Blasts = 0%
Partial remission	All CR criteria if abnormal before treatment except: Bone marrow blasts decreased by ≥50% over pretreatment but still >5% Cellularity and morphology not relevant
Marrow CR†	Bone marrow: ≤5% myeloblasts and decrease by ≥50% over pretreatment† Peripheral blood: if HI responses, they will be noted in addition to marrow CR†
Stable disease	Failure to achieve at least PR, but no evidence of progression for >8 wks

Protocol 2016-0636 Date: 06/03/2019

Page **23** of **39** 

Failure Death during treatment or disease

progression characterized by worsening of cytopenias, increase in percentage of bone marrow blasts, or progression to a more advanced MDS FAB subtype than

pretreatment

Relapse after CR or PR At least 1 of the following: Return to

pretreatment bone marrow blast percentage Decrement of ≥50% from maximum remission/response levels in granulocytes or platelets Reduction in Hgb concentration by ≥1.5 g/dL or

transfusion dependence

Cytogenetic response Complete: Disappearance of the

chromosomal abnormality without

appearance of new ones Partial: At least

50% reduction of the chromosomal

abnormality

Disease progression For patients with: Less than 5% blasts:

≥50% increase in blasts to >5% blasts 5%-10% blasts: ≥50% increase to >10% blasts 10%-20% blasts: ≥50% increase to >20% blasts 20%-30% blasts: ≥50%

increase to >30% blasts

Any of the following: At least 50%

decrement from maximum

remission/response in granulocytes or platelets Reduction in Hgb by ≥2 g/dL

Transfusion dependence

Survival Endpoints: Overall: death from any cause

Event free: failure or death from any cause PFS: disease progression or death from MDS DFS: time to relapse Cause-specific death: death related to MDS

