#### 8.1.1 Phase lb:

The Phase Ib part of the study is performed to assess the safety of telaglenastat in combination with AZA. We will first enroll 6 patients at dose level 0. If only 0 or 1 of 6 patients experiences a DLT, the dose level will be identified as the RP2D. If at least 2 of 6 patients experience DLTs, then the MTD has been exceeded and 6 patients will be treated at the lower dose level (i.e. dose level -1). If at least 2 of 6 patients experience DLTs in dose level -1, the combination may be considered too toxic in this indication and the study may be discontinued. The 6 patients treated at the RP2D level will be evaluated in the Phase II portion. A maximum of 12 patients will be enrolled in the Phase 1b part of the study.

A Toxicity Summary will be submitted to the IND Office Medical Monitor after the first six evaluable patients complete cycle one of study treatment, prior to the Dose modification or Phase II.

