#### 8.2.2. DLT-evaluable:

Unless doses are missed in Cycle 1 due to DLT(s), a patient must receive at least 85% of the planned doses of telaglenastat and at least  $\geq$  5 doses of azacitidine to be considered evaluable for DLTs. If a patient received fewer doses of telaglenastat or AZA in the first 28 days of treatment for reasons other than a DLT, the patient will be considered non-evaluable for DLT and replaced.

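### Section 8.2.3 classes an under-dosed cycle-1 toxicity dropout both ways and lets some early failures leave the response count, and no single Simon denominator is named, so the response rate can overstate activity among treated patients

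*Combined protocol and SAP*

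**What the plan says.** **Evaluability for response (Section 8.2.3).** The first sentence admits anyone with at least one post-baseline disease assessment, and also those "who discontinue study medication early due to study drug-related toxicity will be considered evaluable for efficacy". The second sentence takes out "Patients who discontinue and have not received at least 85% of the telaglenastat doses and at least 5 doses of azacitidine" within cycle 1. It calls them non-evaluable for response and allows, but does not require, their replacement. It makes no exception for toxicity. Section 8.2.2, which uses the same dosing threshold for DLT evaluability, does exempt doses missed because of a DLT.

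**Assessment and failure.** Section 5.2.4 sets the first scheduled on-treatment marrow: "Bone marrow evaluation of tumor/disease burden is required for all patients receiving telaglenastat on cycle 2 day 1". In the Section 6.2.1 response table, the Failure category covers "Death during treatment or disease" progression.

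**Denominator.** Section 4.1.2 plans "A total of 28 evaluable MDS patients", made up of 22 Phase II patients and 6 from Phase 1b. The decision rules in Sections 8.1.2 and 8.3 speak of the first 16 patients and of 28 enrolled. Section 8.3 promises a response rate with a 95% confidence interval but names no population for it. Section 8.1.2 does not say which population its 40% and 60% describe.

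**Phase 1b carry-over.** Under Section 4.1.1, patients who "are removed from study before day 28 for any reason other than toxicity, and have not experienced DLT, will be replaced". Section 8.1.1 adds: "The 6 patients treated at the RP2D level will be evaluated in the Phase II portion". Neither says whether a replaced patient still counts for response.

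**The concern.** Whether a patient enters the response count depends on what happens after treatment starts. Those who can drop out of it are very likely non-responders, so leaving them out pushes the response rate upward at both Simon looks. Because the two sentences of Section 8.2.3 conflict, an under-dosed toxicity dropout could be classed either way once outcomes are known, in a single-arm trial where one or two patients can decide the result. At stake are the response estimate, its interval and the efficacy decision.

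**Working it through.** **1. Patient types against the two sentences of Section 8.2.3**

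| Patient | Sentence 1 | Sentence 2 | Outcome |
|---|---|---|---|
| Stops under-dosed in cycle 1, drug-related toxicity | evaluable | non-evaluable | contradiction |
| Stops under-dosed in cycle 1, progression already documented | evaluable | non-evaluable | contradiction |
| Dies or progresses under-dosed in cycle 1, no assessment | not covered | non-evaluable | out, may be replaced |
| Met dosing threshold, never assessed, did not stop for drug-related toxicity | not covered | does not apply | out by default |
| Met dosing threshold and assessed | evaluable | does not apply | stays in, even if progressing or dying later |

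**2. The plan's own design**

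Inputs from Section 8.1.2: stop if 6 or fewer of 16 respond; efficacious if 15 or more of 28 respond; reference rates 0.40 and 0.60; type I error 10%; power 80%.

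- P(early stop) = P(X ≤ 6), X ~ Bin(16, p).
- P(success) = Σ over x = 7 to 16 of P(X = x) × P(Y ≥ 15 − x), Y ~ Bin(12, p).
- At p = 0.40: early stop 0.5272 (stated 53%); expected size 16 + 12 × (1 − 0.5272) = 21.67 (stated 22); P(success) 0.0989.
- At p = 0.60: P(success) 0.8031.

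The stated design reproduces. The question is only who enters it.

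**3. Effect on the estimate, whichever population 40% describes**

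Assume k treated non-responders are left out and replaced. The documents do not give k, so a range is shown, with exact (Clopper-Pearson) 95% intervals.

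| k | Just-passing result among treated | Rate | 95% CI |
|---|---|---|---|
| 0 | 15/28 | 53.6% | 33.9 to 72.5 |
| 1 | 15/29 | 51.7% | 32.5 to 70.6 |
| 2 | 15/30 | 50.0% | 31.3 to 68.7 |
| 3 | 15/31 | 48.4% | 30.2 to 66.9 |

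**4. Effect on the decision, only if 40% is an all-treated rate**

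With the k replaced non-responders spread evenly, the rate among counted patients is 0.40 × (28 + k)/28. Put into the rule of step 2:

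| k | Rate among counted | P(declare efficacious) | P(early stop) |
|---|---|---|---|
| 0 | 0.4000 | 0.099 | 0.527 |
| 1 | 0.4143 | 0.129 | 0.480 |
| 2 | 0.4286 | 0.164 | 0.434 |
| 3 | 0.4429 | 0.205 | 0.388 |

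Placing all k in one stage gives 0.127 to 0.130, 0.158 to 0.167 and 0.193 to 0.208 for k = 1, 2 and 3. If all fall in stage 2, early stopping stays at 0.527. Under the same condition, a stage-1 pass of 7/16 = 43.8% with two replaced is 7/18 = 38.9% of treated patients (95% CI 17.3 to 64.3), below 40%.

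**The case against.** **A workable reading exists.** Sentence 1 can be taken as the specific rule for toxicity and sentence 2 as covering other discontinuations. That is sensible, but it is not written, and the explicit exception in Section 8.2.2 makes its absence here hard to fill in by inference.

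**The exclusion is narrow.** Patients who met the dosing threshold and were assessed stay in, and replacement for response is optional. This stands, and it limits the likely number.

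**Early failures are not hidden.** Section 6.2.2 calculates event-free survival for all patients, with treatment failure and death as events. Anyone who took one dose of telaglenastat is in the safety population (Section 8.2.1), and first-cycle DLTs feed the stopping rule (Section 8.1.3). A reader might infer that toxicity dropouts vanish from safety monitoring; the documents do not support that. None of these provisions fixes the Simon denominator.

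**No type I error problem is shown.** A reader might infer that the true error rate exceeds 10%, or that 7/18 falls short of the protocol's undesirable rate in any case. Neither follows. Both need 40% to be an all-treated rate, which Section 8.1.2 does not say. If 40% is an evaluable-only rate, the comparison is with 7/16 = 43.8%, and the type I error is unchanged provided evaluability is applied consistently.

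**Conclusion.** The concern holds as a defect of the written rule. Section 8.2.3 contradicts itself for under-dosed cycle-1 toxicity dropouts. It also allows some early deaths, progressions and unassessed patients to leave the response count, and no single denominator governs the Simon decisions and the response rate. Upward bias is possible, not certain.

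The size rests on two assumptions: the number replaced (1 to 3 shown) and that all of them are non-responders. On those, a just-passing result overstates the all-treated rate by 53.6 − 51.7 = 1.9 to 53.6 − 48.4 = 5.2 percentage points. A third assumption, that 40% is an all-treated rate, is needed before the chance of declaring efficacy rises to about 0.13, 0.16 or 0.21.

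A reader might go further and apply the whole allowance of six in Section 8.1, which gives 0.357 if spread evenly and 0.364 if all fall in stage 1. The documents do not support that as an estimate: the allowance is worded around Phase 1b patients and is shared between DLT and response evaluability.

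**What to change.** **(a) Section 8.2.3.** State that sentence 1 prevails for analysis. Any patient treated at the RP2D who stops for drug-related toxicity, who dies or progresses before a documented response, or who met the cycle-1 dosing threshold but has no post-baseline assessment, is evaluable, counts as a non-responder and is not replaced for response. Limit sentence 2 to under-dosed cycle-1 discontinuation for other reasons.

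**(b) Sections 4.1.2, 8.1.1, 8.1.2 and 8.3.** Use that one named denominator for both Simon decisions and for the response rate with its interval. Say that a Phase 1b patient at the RP2D who is replaced only for DLT evaluability still counts for response if (a) is met. State which population 40% and 60% refer to.

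**(c) Section 8.3.** Report alongside it the response rate and 95% CI in all patients who received at least one dose of telaglenastat at the RP2D, counting those without a documented response as non-responders. This also covers the remaining cycle-1 leavers.

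As a separate editorial point, the response summary is triggered at 16 evaluable patients in Section 7.7 and at 15 in Section 8.1.2; reconcile both with the stage-1 size of 16.

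**Cost.** A wording amendment and one extra analysis. The response count stays at 28, so no patients are added. The reported rate may be slightly lower. If 60% was meant to exclude early failures, power falls. With a share f of counted patients added as non-responders, the rate is 0.60 × (1 − f): 0.582, 0.570 and 0.540 for f = 3%, 5% and 10%, with power 0.745, 0.702 and 0.583 against 0.803. The amendment should say so.

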#### 8.3. Analysis Plan:

During Phase II portion, if 6 or fewer patients out of the first 16 patients achieve response, enrollment will be halted. If 7 or more out of the first 16 patients achieve response, accrual will continue until a total of 28 patients have been enrolled. If 15 or more out of these 28 patients achieve response, the treatment will be considered efficacious and worthy of further investigation. The rates of response (CR+PR+mCR+HI) to therapy will be estimated along with the 95% confidence interval. The Kaplan-Meier method will be used to estimate the probabilities of event-free survival (EFS), overall survival (OS) and duration of response. Log-rank tests will be used to compare among subgroups of patients in terms of EFS, OS or duration of response. Anti-tumor activity, PDn markers, exploratory biomarkers and drug exposure levels will be summarized graphically and with descriptive statistics. Safety data will be summarized using frequency and percentage, by category and severity.

Protocol 2016-0636 ate: 06/03/2019

Page **36** of **39** 

## **APPENDIX A:** CYP2C9 Substrates with a narrow therapeutic index\*

- S-Warfarin (anticoagulant)
- Phenytoin (antiepileptic)

\*Narrow therapeutic index is defined as "CYP substrates with narrow therapeutic range refers to drugs whose exposure-response relationship indicates that small increases in their exposure levels by the concomitant use of CYP inhibitors may lead to serious safety concerns (e.g., Torsades de Pointes)."

http://www.fda.gov/drugs/developmentapprovalprocess/developmentresources/druginter actionslabeling/ucm093664.htm

### **Other CYP2C9 Substrates**

- NSAIDs (analgesic, antipyretic, anti-inflammatory)
  - o celecoxib
  - lornoxicam
  - o diclofenac
  - o ibuprofen
  - o naproxen
  - ketoprofen
  - o piroxicam
  - meloxicam
  - o suprofen
- fluvastatin (statin)
- sulfonylureas (antidiabetic)
  - glipizide
  - glibenclamide
  - o glimepiride
  - o tolbutamide
  - o glyburide
- irbesartanlosartan
- sildenafil (in erectile dysfunction)
- terbinafine (antifungal)
- amitriptyline (tricyclic antidepressant)
- fluoxetine (SSRI antidepressant)
- nateglinide (antidiabetic)
- rosiglitazone (antidiabetic)
- tamoxifen (SERM)
- torasemide (loop diuretic)ketamine

NCT ID: NCT03047993 Protocol 2016-063 Date: 06/03/2019

Page **39** of **39** 

## **APPENDIX B: PK Collection of Specimens**

Approximately 2ml of blood will be collected via peripheral venipuncture into an EDTA tube (lavender top). This blood sample will be used to measure concentrations of telaglenastat (CB-839) of each pharmacokinetic blood collection. The time of collection must be noted in the source documents and eCRFs.

For collecting specimens, the following protocol should be followed:

- Label a 3.0 mL K2EDTA vacutainer tube.
- Label 2 cryovials.
- Prepare an ice bucket.
- Draw blood into the 3.0 mL vacutainer tube. Ensure that tube is filled with a minimum of 2 mL of blood.
- Samples should be thoroughly mixed by completely and gently inverting the tube 8 times. If a complete 2 mL volume of blood was not obtained, please discard sample and re-collect with a fresh vacutainer.
- The whole blood samples should be placed on ice immediately after collection.
   Try not to wet the label.
- Plasma should be prepared within 30 minutes of collection by centrifuging the blood samples at 2000 x g for 10 minutes at 4°C.
- Split the resultant plasma into two aliquots of approximately equal amounts (at least 0.3 mL) and transfer into the two labeled cryovials.
- Place each of the three samples immediately into the cryobox and store at 70°C until shipment.

Note: PK assay will be conducted at a central laboratory where the assay for CB-839 has been validated. Details are given below and in the laboratory manual:

Pharmacokinetic analysis will be carried out by central lab

Intertek Pharmaceutical Services

Attn: Sample Accessioning
Address: [name]

[name]

[contact] [contact]

Email: [contact]

All plasma samples will be analyzed for telaglenastat (CB-839) by using a validated liquid chromatography tandem mass spectrometry (LC-MS/MS) method of appropriate specificity and sensitivity according to Good Laboratory Practices (GLPs).
